6.3 Dose modifications

6.3.1 Dose modification and dose delay

For patients who do not tolerate the protocol-specified dosing schedule, dose adjustments are permitted in order to allow the patient to continue the study treatment. The following guidelines need to be applied:

These changes must be recorded on the Dosage Administration Record CRF.

All dose modifications should be based on the worst preceding toxicity.

Each patient is only allowed 2 dose reductions as showed in [Table 6-7](#).

If a patient requires a dose interruption of > 14 days from the intended day of the next scheduled dose, then the patient must be discontinued from the study. Patients who discontinue the study for a study related adverse event or an abnormal laboratory value must be followed as described in [Table 6-](#).

Table 6-7 Dose adjustment of HH2710

	HH2710(mg)
Dose	Starting Dose
First dose reduction	75% of the starting dose*
Second dose reduction	50% of the starting dose*

* The actual reduced dose should take into account the drug specification

Adjust reference values in the table below according to the CTCAE V5.0 used in the study.

The criteria for interruption and re-initiation of HH2710 treatment is showed in [Table 6-](#)

Table 6-8 Criteria for interruption, re-initiation of HH2710 treatment and permanently discontinuation

Recommended dose modifications for HH2710	
Worst toxicity	Recommended dose modifications any time during a cycle of therapy, including intended day of dosing^b
CTCAE Grade^a (value)	
No toxicity	Maintain dose level
Investigations (Hematologic)	
Neutropenia (ANC)	
Grade 1 (ANC < LLN - 1500/mm ³)	Maintain dose level
Grade 2 (ANC < 1500 - 1000/mm ³)	Maintain dose level
Grade 3 (ANC < 1000 - 500/mm ³)	Discontinue HH2710: 
 - If elevation lasts for \leq 7 days: Resume treatment at same dose level - If elevation lasts for >7 days: Resume treatment at ≥ 1 dose level
Grade 4 (ANC < 500/mm ³)	Discontinue dose until resolved to \leq Grade 2, then ≥ 1 dose level 
If there is no recovery to \leq Grade 2 or there is recurrent grade 3 or 4 neutropenia, G-CSF/Neulasta may be given at physician discretion.
 
If no recovery to \leq Grade 2, permanently discontinue HH2710

Thrombocytopenia	
Grade 1 (PLT < LLN - 75,000/mm ³)	Maintain dose level
Grade 2 (PLT < 75,000 - 50,000/mm ³)	Maintain dose level

Recommended dose modifications for HH2710	

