Worst toxicity CTCAE Grade^a (value)	Recommended dose modifications any time during a cycle of therapy, including intended day of dosing^b
Grade 3 (PLT < 50,000 - 25,000/mm ³)	
Discontinue dose until resolved to \leq Grade 2, then:
 
 - If resolved in \leq 7 days, then maintain dose level - If resolved in $>$ 7 days, then \downarrow 1 dose level 
If no recovery to \leq Grade 2, permanently discontinue HH2710
 
Second occurrence: discontinue until toxicity resolves to \leq Grade 2, reduce to by another dose level.
 
3rd occurrence permanently discontinue HH2710.

Grade 4 (PLT < 25,000/mm ³)	
Discontinue dose until resolved to \leq Grade 2, then \downarrow 1 dose level
 
If no recovery to \leq Grade 2, permanently discontinue HH2710
 
Second occurrence: discontinue until toxicity resolves to \leq Grade 2, reduce to by another dose level.
 
3rd occurrence permanently discontinue HH2710.

Febrile neutropenia (ANC < 1.0 x 10 ⁹ /L, fever \geq 38.5°C)	Discontinue dose until resolved, then \downarrow 1 dose level
First episode	
Discontinue HH2710 until afebrile and ANC $>$ 1000.
 
Add Filgrastim/Neulasta per physician discretion.

Second episode	
Discontinue HH2710 until afebrile and ANC $>$ 1000.
 
Add Filgrastim/ Neulasta per treating physician discretion.
 
Restart HH2710 at dose reduced by one dose level and monitor as clinically.

Recommended dose modifications for HH2710	
Worst toxicity CTCAE Grade^a (value)	Recommended dose modifications any time during a cycle of therapy, including intended day of dosing^b
Third episode	Discontinue HH2710 until afebrile and ANC >1000. Add Filgrastim/ Neulasta per treating physician discretion. Restart HH2710 reduced by another dose level and monitor as clinically indicated.
Fourth episode	Permanently discontinue HH2710 and continue follow-up protocol.
Investigations (Hematologic) for LCH	Manage as per institutional standard or global guidance.
Investigations (Renal)	
Serum creatinine	
Grade 1 (> ULN - 1.5 x ULN)	Maintain dose level
Grade 2 (>1.5 - 3.0 x baseline; > 1.5 - 3.0 x ULN)	Discontinue dose until resolved to \leq Grade 1 or baseline, then maintain dose level
Grade 3 (>3.0 x baseline; > 3.0 - 6.0 x ULN)	Permanently discontinue HH2710
Grade 4 (> 6.0 x ULN)	Permanently discontinue HH2710
Investigations (Hepatic)*	
Bilirubin	

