≥ Grade 3 ocular/vision symptoms interfering with ADL (Activities of daily living) or requiring medical intervention	Permanently discontinue HH2710.
Vascular disorders	
Hypertension	
Grade 1 and 2	Maintain dose level
Grade 3	Discontinue dose until resolved ≤ Grade 1, then ↓ 1 dose level
Grade 4	Permanently discontinue HH2710
Gastrointestinal	
Pancreatitis	
Grade 2	Maintain dose level
Grade ≥ 3	Permanently discontinue HH2710
Diarrhea***	
Grade 1 and 2	Maintain dose level, but initiate anti-diarrhea therapy

Recommended dose modifications for HH2710	
Worst toxicity CTCAE Grade^a (value)	Recommended dose modifications any time during a cycle of therapy, including intended day of dosing^b
Grade 3	Discontinue dose until resolved to \leq grade 1, then \downarrow 1 dose level
Grade 4	Permanently discontinue HH2710
Skin and subcutaneous tissue disorders	
Rash/photosensitivity	
Grade 1 and 2	Maintain dose level. Consider to initiate institute appropriate skin toxicity therapy (such as antihistamines, topical corticosteroids and low-dose systemic corticosteroids)
Grade 3, despite skin toxicity therapy	Discontinue dose until resolved to Grade \leq 1, then: 
 – If resolved in \leq 7 days, then \downarrow 1 dose level – If resolved in $>$ 7 days, then discontinue HH2710
Grade 4, despite skin toxicity therapy	Permanently discontinue HH2710
General disorders and administration site conditions	
Fatigue/ Asthenia	
Grade 1 or 2	Maintain dose level
Grade 3	Discontinue dose until resolved to \leq grade 1, then: 
 – If resolved in \leq 7 days, then maintain dose level – If resolved in $>$ 7 days, then \downarrow if resolved in
Other adverse events****	

Recommended dose modifications for HH2710	
Worst toxicity CTCAE Grade^a (value)	Recommended dose modifications any time during a cycle of therapy, including intended day of dosing^b
Grade 1 or 2	Maintain dose level
Grade 3	Discontinue dose until resolved to \leq grade 1, then \downarrow 1 dose level
Grade 4	Permanently discontinue HH2710 Discontinue dose for \geq grade 3 vomiting or grade 3 nausea only if the vomiting or nausea cannot be controlled with optimal antiemetic (as per local practice)

All dose modifications should be based on the worst preceding toxicity.

^a Common Toxicity Criteria for Adverse Events (CTCAE V5.0)

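### Table 6-8 conflicts on the restart dose after a first febrile neutropenia episode, and one of its two readings runs past the two-reduction limit

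*Protocol*

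**What the plan says.** Section 6.3.1 of the protocol sets the limit: "Each patient is only allowed 2 dose reductions as showed in" Table 6-7. That table gives two reduced doses, 75% and 50% of the dose on which the patient began.

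The febrile neutropenia block of Table 6-8 (Section 6.3.1) has five rows:

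- **Heading row:** "Discontinue dose until resolved, then" one dose level down. No episode number is attached.
- **First episode:** hold until the fever has gone and ANC exceeds 1000. "Add Filgrastim/Neulasta per physician discretion". No restart dose is given.
- **Second episode:** same hold. "Restart HH2710 at dose reduced by one dose level and monitor as clinically".
- **Third episode:** same hold. "Restart HH2710 reduced by another dose level and monitor as clinically indicated".
- **Fourth episode:** "Permanently discontinue HH2710 and continue follow-up protocol".

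Nothing says whether the heading row governs the first episode or loosely summarises the rows below it. The neutropenia and thrombocytopenia heading rows carry no instruction of their own.

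Table 6-9 (Section 6.3.2) sets a different recovery level. It has neutropenia of Grade 3 or worse tested until Grade 1 or better before treatment restarts. On the grading printed in Table 6-8, that means an ANC of at least 1500/mm3.

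**The concern.** Febrile neutropenia of any grade is a dose-limiting toxicity under Table 6-6, so the handling of a first episode should not depend on which row a site reads. One site can follow the heading row and go down a level. Another can take the silent first-episode row as permission to resume at full dose. Each can point to the same block of the table.

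The first site meets a second problem later. If the patient has a third episode, the third-episode row tells it to reduce again, although both permitted reductions are spent and Table 6-7 defines no lower dose. At stake are consistent dosing after a serious toxicity and a clean reading of dose-reduction and exposure data.

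**Working it through.** **Inputs.** The limit of 2 reductions per patient (Section 6.3.1); reduced doses of 75% and 50% (Table 6-7); the five febrile neutropenia rows (Table 6-8). One assumption is needed: that one dose level in Table 6-8 equals one step in Table 6-7.

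**The plan's own figure.** Table 6-7 has two steps below the starting dose, which agrees with the stated limit of 2.

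**Reductions by reading, episodes 1 to 3.**

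- Heading row applied at episode 1, then the episode rows: 1 + 1 + 1 = 3.
- Episode rows alone: 0 + 1 + 1 = 2.
- Proposed sequence: 1 + 1 = 2, then stop.

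**Restart dose as a percentage of the patient's starting dose.**

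| Reading | After episode 1 | After episode 2 | After episode 3 |
|---|---|---|---|
| Heading row plus episode rows | 75 | 50 | none defined |
| Episode rows alone | 100 (inferred) | 75 | 50 |
| Proposed | 75 | 50 | stop |

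At 600 mg QD, 0.75 × 600 = 450 and 0.50 × 600 = 300. The first restart is then 450 mg on one reading and 600 mg on the other. The episode-rows reading is 1.00/0.75 = 1.33 times the heading reading after episode 1, and 0.75/0.50 = 1.50 times after episode 2.

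**Which first restart fits the rest of the table?** The block covers ANC below 1000/mm3, which Table 6-8 grades as 3 or 4. Twelve other rows allow a restart after a Grade 3 event:

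- Six reduce by one level at the first restart: bilirubin, cardiac general, hypertension, diarrhea, rash, and other adverse events ("Discontinue dose until resolved to" Grade 1 or better, then one level down).
- Six keep the dose only if the event clears within 7 days: neutropenia, thrombocytopenia, AST/ALT, amylase/lipase, QTc, and fatigue. They say so explicitly; the neutropenia row, for example, has "Resume treatment at same dose level". In the neutropenia and fatigue rows the branch for more than 7 days is garbled in the extracted text and is read here as one level down.

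So 6 + 6 = 12 rows, and none allows a full-dose restart regardless of duration. Grade 4 thrombocytopenia already follows the proposed pattern: one level down, another level down, stop at the third occurrence. Grade 4 neutropenia without fever also appears to restart one level down, although its symbol is garbled. If so, the full-dose reading would give a patient with ANC below 500 and fever a higher restart dose than one with the same count and no fever.

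**The case against.** A reader might infer that the table simply orders three reductions, and that the missing first-episode dose is a second, separate defect. The documents do not support that. The two problems belong to different readings: if the heading row governs episode 1, the dose is stated and the count is three; if it does not, the count is two and the dose is unstated. The numbered rows alone fit Section 6.3.1 and Table 6-7 exactly, so the heading entry may be stray text. A further reading also stays within two: apply the heading row at episode 1 and measure the second-episode reduction from the starting dose, giving 1 + 0 + 1.

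It can also be said that the third-episode order is not truly unworkable. The cap is per patient, so any reduction row can be reached after both reductions are used, and the natural consequence is to stop. That stands, although the protocol does not say it.

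For a full-dose first restart, one can cite the Grade 3 neutropenia row, which resumes at the same dose after 7 days or less, and the Grade 2 creatinine and ejection-fraction rows, which maintain the dose after a hold. The neutropenia rule is conditional on duration, is not linked to the febrile rows and does not cover Grade 4. The other two concern lower grades. They show that full dose is a possible choice, not that it is the one made here.

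Finally, the table is headed as recommendations. Section 6.3.1 nevertheless presents these guidelines as ones to be applied.

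**Conclusion.** The conflict is real but minor. The restart dose after a first febrile neutropenia episode is either one level down (heading row) or full dose (inferred from the episode rows). The first choice leads to three reductions against a limit of two if a third episode occurs; the second leads to two. The dose figures rest on equating a dose level with a Table 6-7 step. The conflict between the rows does not.

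It would be wrong to infer an effect on dose-finding or on the Phase II design. The toxicity criterion is met when febrile neutropenia occurs, whatever the restart dose, and no sample size, stopping boundary or error rate changes. The event should be uncommon: Section 1.2.2 describes most hematologic events as Grade 1 or 2, though the documents give no count of febrile neutropenia. The over-limit case needs three episodes in one patient. LCH patients are outside it, since Table 6-8 leaves their hematologic toxicity to institutional or global guidance. SAP Section 7 says the program is stopped, so the benefit is confined to patients still on treatment and to any reuse of this text.

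**What to change.** In the febrile neutropenia block of Table 6-8, remove the instruction from the heading row and write one sequence:

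- **First episode:** hold, growth factor at the physician's discretion, restart at 75%.
- **Second episode:** same hold, restart at 50%.
- **Third episode:** permanently discontinue.
- Delete the fourth-episode row.

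State that the limit counts reductions for any toxicity. A patient who has already used one takes the next step, and a patient who has used both stops.

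This follows the heading row and the Grade 4 thrombocytopenia row. Its cost is discontinuation one episode earlier than the episode rows alone allow. Writing a same-dose restart for episode 1 and keeping the remaining rows would also remove the conflict and would keep that extra episode, but it fits less well with the table's other Grade 3 and 4 rows. Deleting the heading instruction alone is not enough, because the first restart dose would remain unstated.

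In the same edit, make the recovery threshold agree with Table 6-9: ANC above 1000 in one table, Grade 1 or better in the other. Adopting the stricter level would lengthen some holds, and Section 6.3.1 discontinues patients whose interruption exceeds 14 days, so the choice should be deliberate.

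The change touches five rows of one table, plus the threshold wording. It needs no extra patients, visits or procedures.

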Cohort	A group of newly enrolled patients treated at a specific dose and regimen (i.e. treatment group) at the same time
Cycles	Number and timing or recommended repetitions of therapy are usually expressed as number of days (e.g.: q21 days)
Dose level	The dose of drug given to the patient (total daily or weekly etc.)
Enrollment	Point/time of patient entry into the study; the point at which informed consent must be obtained (i.e. prior to starting any of the procedures described in the protocol)
Investigational drug	The study treatment whose properties are being tested in the study; this definition is consistent with US CFR 21 Section 312.3 and is synonymous with “investigational new drug.”
Investigational treatment	Drug whose properties are being tested in the study as well as their associated placebo and active treatment controls (when applicable). This also includes approved drugs used outside of their indication/approved dosage, or that are tested in a fixed combination. Investigational treatment generally does not include other study treatments administered as concomitant background therapy required or allowed by the protocol when used in within approved indication/dosage
Medication number	A unique identifier on the label of each study treatment package which is linked to one of the treatment groups of a study
Other study treatment	Any drug administered to the patient as part of the required study procedures that was not included in the investigational treatment
Patient Number /Subject Number (Patient No.)	A unique identifying number assigned to each patient/subject /healthy volunteer who enrolls in the study
Period	A subdivision of the study timeline; divides stages into smaller functional segments such as screening, baseline, titration, washout, etc.
Premature patient withdrawal	Point/time when the patient exits from the study prior to the planned completion of all study treatment administration and/or assessments; at this time all study treatment administration is discontinued and no further assessments are planned, unless the patient will be followed for progression and/or survival

Stage related to study timeline	A major subdivision of the study timeline; begins and ends with major study milestones such as enrollment, randomization, completion of treatment, etc.

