Stage in cancer	The extent of a cancer in the body. Staging is usually based on the size of the tumor, whether lymph nodes contain cancer, and whether the cancer has spread from the original site to other parts of the body
Stop study participation	Point/time at which the patient came in for a final evaluation visit or when study treatment was discontinued whichever is later
Study treatment	
Includes any drug or combination of drugs in any study arm administered to the patient (subject) as part of the required study procedures, including placebo and active drug run-ins.
 
In specific examples, it is important to judge investigational treatment component relationship relative to a study treatment combination; study treatment in this case refers to the investigational and non-investigational treatments in combination.

Study treatment discontinuation	Point/time when patient permanently stops taking study treatment for any reason; may or may not also be the point/time of premature patient withdrawal
Treatment group	A treatment group defines the dose and regimen or the combination and may consist of 1 or more cohorts. Cohorts are not expanded; new cohorts are enrolled.
Variable	Identifier used in the data analysis; derived directly or indirectly from data collected using specified assessments at specified time points

Protocol summary

Protocol number	HH2710-G101
Title	A First-in-Human, Open Label, Phase I/II Study to Evaluate the Safety, Tolerability and Pharmacokinetics of HH2710 in Patients with Advanced Tumors
Sponsor	Haihe Biopharma Co., Ltd.
Phase	Phase I/II
Location and sites	Multinational, Multicenter
Purpose and rationale	The purpose of this study is to characterize the safety, tolerability, pharmacokinetics (PK), pharmacodynamics (PD) and preliminary efficacy of HH2710 administered orally in adult patients with advanced tumors.

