Grade 1 (>ULN - 1.5 x ULN if baseline was normal; > 1.0 - 1.5 x baseline if baseline was abnormal)	Maintain dose level

Recommended dose modifications for HH2710	
Worst toxicity CTCAE Grade^a (value)	Recommended dose modifications any time during a cycle of therapy, including intended day of dosing^b
Grade 2 (>1.5 - 3.0 x ULN if baseline was normal; >1.5 - 3.0 x baseline if baseline was abnormal)	Discontinue dose until resolved to \leq Grade 1, then: 
 - If resolved in \leq 7 days, then maintain dose level - If resolved in > 7 days, then \downarrow 1 dose level
Grade 3 (>3.0 - 10.0 x ULN if baseline was normal; >3.0 - 10.0 x baseline if baseline was abnormal)	Discontinue dose until resolved to \leq Grade 1, then: 
 - If resolved in \leq 7 days, then \downarrow 1 dose level - If resolved in > 7 days, then discontinue patient from study drug treatment
Grade 4 (>10.0 x ULN if baseline was normal; >10.0 x baseline if baseline was abnormal)	Permanently discontinue HH2710
AST or ALT	
Grade 1 (>ULN - 3.0 x ULN if baseline was normal; 1.5 - 3.0 x baseline if baseline was abnormal)	Maintain dose level
Grade 2 (>3.0 - 5.0 x ULN if baseline was normal; >3.0 - 5.0 x baseline if baseline was abnormal)	Maintain dose level
Grade 3 (>5.0 - 20.0 x ULN if baseline was normal; >5.0 - 20.0 x baseline if baseline was abnormal)	Discontinue dose until resolved to \leq Grade 1 (or \leq Grade 2 if liver metastases present), then: 
 - If resolved in \leq 7 days, then maintain dose level - If resolved in > 7 days, then \downarrow 1 dose level
Grade 4 (>20.0 x ULN if baseline was normal; >20.0 x baseline if baseline was abnormal)	Permanently discontinue HH2710

Recommended dose modifications for HH2710	
Worst toxicity CTCAE Grade^a (value)	Recommended dose modifications any time during a cycle of therapy, including intended day of dosing^b
ALT/AST > 3 ULN and concomitant TBL > 2 ULN in the absence of evidence of biliary obstruction (i.e., significant elevation of ALP) or some other explanation of the injury (e.g., viral hepatitis, alcohol hepatitis) of any duration (i.e. Hy's law)	Permanently discontinue HH2710
Investigation (metabolic)**	
amylase and/or lipase elevation	
Grade 1 (> ULN - 1.5 x ULN)	Maintain dose level
Grade 2 (>1.5-2.0xULN; >2.0-5.0xULN and asymptomatic)	Maintain dose level

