6.3.2 Follow-up for toxicities

Patients whose treatment is interrupted or permanently discontinued due to an adverse event or clinically significant laboratory value, must be followed up at least once a week (or more frequently if required by institutional practices, or if clinically indicated) for 4 weeks, and subsequently at approximately 4-week intervals, until resolution or stabilization of the event, whichever comes first.

Appropriate clinical experts such as ophthalmologist, endocrinologist, dermatologist, psychiatrists etc. should be consulted as deemed necessary.

Table 6-9 outlines the follow-up evaluation recommended for toxicities of specific types and CTCAE grades.

Table 6-9 Follow-up evaluations for selected toxicities

TOXICITY	FOLLOW-UP EVALUATION
Blood and lymphatic system disorders	Test twice weekly until \leq CTCAE grade 1, then restart treatment. Continue to test weekly until resolution to baseline or stabilization.
Investigations (hematologic) Neutropenia \geq CTCAE grade 3 Thrombocytopenia \geq CTCAE grade 3	Test twice weekly until \leq CTCAE grade 1, then restart treatment. Continue to test weekly until resolution to baseline or stabilization. Perform physical exam for check on bruising in case of major thrombocytopenia.
Investigations (hepatic) Total bilirubin $\geq 2 \times$ ULN OR AST/ALT \geq CTCAE grade 3 ($> 5 \times$ ULN)	Test twice weekly until \leq CTCAE grade 1, (or \leq CTCAE grade 2 for ALT/AST if liver metastases are present) then restart treatment. Continue to test weekly until resolution to baseline or stabilization. Patients with total bilirubin $>$ ULN (any duration) should have fractionation of bilirubin into total/direct or indirect/direct components and any additional work-up as clinically indicated by these results. Follow-up of hyperbilirubinemia should proceed as per the guidelines above, irrespective of the results of fractionation.
Investigations (metabolic) Amylase or lipase \geq CTCAE grade 3	Test twice weekly until \leq CTCAE grade 2, then restart treatment. Continue to test weekly until resolution to \leq CTCAE grade 1 or stabilization. A CT scan or equivalent imaging procedure to assess the pancreas, liver, and gallbladder is recommended within 7 days of the first occurrence of any \geq

	CTCAE grade 3 result, to exclude disease progression or potential other liver disease. In patients with serum triglycerides \geq 500 mg/dL, urine amylase also needs to be tested.

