6.4.3 Prohibited concomitant therapy

Anticancer therapy (chemotherapy, biologic or radiation therapy, surgery or Chinese medicine/Chinese patent medicine with anti-tumor effect) other than the study treatments must not be given to patients while the patient is on the study. If such agents are required for a patient, then the patient must be discontinued from the study.

In vitro data indicate Drug HH2710 is metabolized primarily by CYP3A, therefore strong inhibitors of CYP3A4 (e.g., clarithromycin, itraconazole, ketoconazole, telithromycin, etc.) and strong CYP3A4 inducers (e.g., carbamazepine, rifampicin, St. John's wort, etc.) should be avoided. Gastric acid reducing agents and sensitive substrates of CYP2C8, CYP2C9, and CYP2C19 also should be avoided. Refer to [**Appendix 14.7**](#) for a list of prohibited medications. This list may not be comprehensive.

Current treatment with agents including vitamins, supplements, and herbal supplements that are metabolized solely through CYP3A4 should be prohibited.

In vitro data indicate HH2710 is a potential P-gp substrate. Strong P-gp inhibitor will likely increase the exposure level of HH2710. Strong P-gp inhibitor should be avoided (Refer to [**Appendix 14.8**](#)).

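### Sections 6.3.1 and 6.4.3 remove patients from the study where the follow-up rules and the SAP stop treatment only; read literally, 6.3.1 could cost response-confirmation scans

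*Protocol*

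**What the plan says.** Two operative sentences take the patient off the study:

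- Protocol 6.3.1, for a dose interruption of more than 14 days: "then the patient must be discontinued from the study".
- Protocol 6.4.3, on anticancer therapy other than study treatment: "If such agents are required for a patient, then the patient must be discontinued from the study".

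Other text stops treatment only:

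- Protocol 7.1.4.1 lists concurrent antineoplastic therapy, the 6.4.3 trigger, among the reasons to stop study treatment, and states that the end-of-treatment (EOT) visit does not end the study.
- Protocol 7.1.5.1 continues 6-weekly CT or MRI in patients who stop without progression, until progression or new systemic therapy. Section 7.1.5.2 requires survival follow-up after treatment stops, and moves patients who start new therapy before the EOT visit straight to it.
- SAP Appendix E ends a subject's participation only at death, withdrawal of consent or loss to follow-up.

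The protocol treats the two kinds of stop as different. In the glossary, stopping treatment "may or may not also be the point/time of premature patient withdrawal", and after premature withdrawal "no further assessments are planned, unless the patient will be followed for progression and/or survival". Table 6-8, inside Section 6.3.1, uses treatment-only wording: "then discontinue patient from study drug treatment" for a slow-resolving Grade 3 bilirubin rise, and "Permanently discontinue HH2710 and continue follow-up protocol" for a fourth febrile neutropenia.

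**The concern.** The follow-up that 6.3.1 itself preserves concerns toxicity. Its next sentence begins "Patients who discontinue the study for a study related adverse event or an abnormal laboratory value must be followed as described in", and Section 6.3.2 says patients stopped for an adverse event or laboratory value "must be followed up at least once a week". Contact therefore continues after an adverse event, but neither text sets RECIST scans or survival calls. A site could take this as the whole of the remaining follow-up.

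What would be at stake under 6.3.1:

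- **ORR.** SAP Appendix E counts only confirmed CR or PR, and Protocol 7.2.5 asks for confirmation at about 6 weeks (±7 days). In the RECIST appendix, a PR followed by a non-evaluable time point becomes SD or NE. Phase II patients are not replaced (Protocol 7.1.4.3) and every dosed patient is in the efficacy set (SAP 6.1), so an unconfirmed responder counts as a non-responder.
- **PFS and DoR.** The SAP's PFS counts progression after a patient has come off HH2710, which needs the later scans. Protocol 10.6.8 censors DoR on removal from the study.
- **Survival status**, which feeds the 1-year OS rate.

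The loss under 6.4.3 is smaller. Scans already end at new systemic therapy (7.1.5.1), and PFS and DoR are already censored at alternative therapy (SAP Appendix A, row 7). What could be lost is mainly the survival calls, plus scans after local treatment such as radiation or surgery.

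**Working it through.** The plan gives no figure on this point. The stated Phase II power was recomputed only to confirm that the fix leaves it alone. The exact two-stage binomial probability of at least 2 responses in 23 and at least 4 in 36 is 0.8195 at a response rate of 0.16 (plan: 0.8201) and 0.0936 at 0.05 (plan: at most 0.10). A wording change alters neither.

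The useful check is one of timing: when would a literal 6.3.1 remove a responder before confirmation is possible?

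**Inputs**

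- Scans at Cycle 3 Day 1 and every 2 cycles (7.2.5), with 21-day cycles: Day 43, 85, 127. Call the scan showing the first PR *S*.
- Confirmation at about 6 weeks ±7 days (7.2.5): *S*+35 to *S*+49.
- *I* = intended day of the first missed dose, so the last dose is on *I*−1. The 14-day limit is passed at *I*+15 (6.3.1).
- EOT visit, with a scan, within 7 days of the decision to stop (7.1.4.1): *I*+15 to *I*+22. The Table 7-1 rule, 7 days from last dose, would give an earlier date and help no one.
- Off-treatment scans every 6 weeks ±7 days after the last dose (7.1.5.1, 7.2.5).

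**Literal 6.3.1**

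- Still on study at the PR scan: *I*+15 ≥ *S*, so *I* ≥ *S*−15.
- Latest EOT scan still before the window: *I*+22 < *S*+35, so *I* ≤ *S*+12.
- Affected starts run from *S*−15 to *S*+12, which is 12+15+1 = 28 days.

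| First PR (*S*) | Confirmation window | Affected interruption starts |
|---|---|---|
| Day 43 | Day 78–92 | Day 28–55 |
| Day 85 | Day 120–134 | Day 70–97 |
| Day 127 | Day 162–176 | Day 112–139 |

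For *S* = 43, a start on Day 56–62 depends on when the EOT visit falls. From Day 63, removal (63+15 = 78) is no earlier than the window opens.

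**Section 7.1.5 followed instead, *S* = 43**

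- First follow-up scan: (*I*−1)+42±7, that is *I*+34 to *I*+48, nominally *I*+41.
- With the visit window, it can reach Day 78–92 when *I*+48 ≥ 78, so *I* ≥ 30. Day 30–55 is 26 of the 28 start days.
- On the nominal date, 78 ≤ *I*+41 ≤ 92 gives *I* = 37–51, which is 15 of 28.

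The two readings therefore yield different data for the primary endpoint.

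**Per patient:** 1/36 = 2.8 percentage points of confirmed ORR in Cohort 1 or 2.

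**The case against.** The strongest reply is that the protocol read as a whole already settles the matter. Section 7.1.5.1 covers anyone who stops treatment without progression, and its stopping conditions do not include a dose interruption. Section 6.1.2 cites 6.3 as a criterion for ending treatment. Section 7.1.4.1 is headed as discontinuation of the study but opens by describing termination of treatment, so the vocabulary is loose throughout. Its two lists of reasons are not exhaustive, and the glossary's withdrawal entry makes an exception for patients followed for progression or survival. A Table 6-8 footnote allows earlier resumption case by case, which can avoid the 14-day trigger. On nominal dates, 13 of the 28 start days miss the window even when 7.1.5 is followed. The 6.4.3 part is thin, and the SAP says the program has stopped.

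Most of this stands, and it makes the harm conditional: a site reading every section would probably keep scanning. It does not remove the contradiction. Section 6.3.1 is a mandatory instruction at the point where a site handles a long interruption, it preserves only toxicity follow-up, and Section 12 gives investigators no authorised departures. Nothing ranks 7.1.5 above it.

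It is also right that no go/no-go effect should be inferred. SAP Sections 3.2 and 5 count SD of at least 6 weeks towards the decision thresholds, so an unconfirmed PR may still count there.

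**Conclusion.** The concern holds. Two mandatory sentences say study where the visit schedule, the follow-up sections and the SAP require treatment, and no text says which governs. Under a literal 6.3.1, a patient with a first PR whose interruption starts in a 28-day span around that scan leaves before confirmation is possible. Following 7.1.5 makes confirmation possible for 26 of those 28 start days, or 15 on nominal dates. Each lost confirmation costs 2.8 points of confirmed ORR in a cohort of 36.

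The day counts assume nominal visit days and removal as soon as the 14-day limit is passed. The documents give no rate of interruptions longer than 14 days among unconfirmed responders, so the number affected and any bias in ORR, PFS or DoR cannot be computed. The harm arises only if a site applies the sentence literally, and early termination (SAP Section 7) limits its practical effect on Phase II. The change should be made, but no design figure is wrong.

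**What to change.** In Sections 6.3.1 and 6.4.3, replace the instruction to take the patient off the study with: *discontinued from study treatment and followed per Section 7.1.5*. Keep the 14-day limit and the prohibition on other anticancer therapy. Sections 4.3, 4.4, 7.1.4.1 and 7.1.4.2 need no change.

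The cost is two protocol sentences. No procedure is added, because the scans and survival calls are already in Sections 7.1.5 and 7.2.5 and Table 7-1. Sample size, stopping boundaries and power are unaffected.
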